 - j. The specific laboratory tests required for chemistry, hematology and urinalysis are listed in [Table 7](#). Triglycerides will only be collected at Screening and at the Final Visit. Amylase and lipase will be collected at Screening, Cycle 1 Day 15, and Final Visit. For any subjects who are at high risk for tumor lysis syndrome (TLS) during Cycle 2 and beyond, additional samples for hematology and chemistry may be collected as per the management guidelines in Section [6.7.4](#).
 - k. Assessment for tumor response will be performed at the end of Cycle 2, end of Cycle 4, end of every 4 cycles through Cycle 20 (i.e., C8, C12, C16, C20), end of every 8 cycles thereafter (i.e., C28, C36, C44. . .) and at the Final Visit. Analysis of peripheral blood for tumor response will be performed on Day 1 (pre-dose) of the following cycle for every tumor assessment.
 - l. A CT scan will be performed at Screening (within 21 days prior to study drug administration).
 - m. Assessments for tumor response will be repeated 2 months after NCI-WG (1996) criteria for a complete remission (CR) are first met and/or at least 2 months after IWCLL updated NCI-WG (2008) criteria for a complete remission (CR or CRi) or partial remission (PR) are first met.
 - n. If clinical and laboratory criteria for a CR or PR are met), a bone marrow aspirate/biopsy and CT scan should be performed at least 2 months after the criteria are first met in order to confirm a CR or PR. A bone marrow aspirate/biopsy will be performed at the end of Cycle 8 (for all subjects regardless of response) if the subject is continuing to receive ABT-263.
 - o. Bone marrow aspirate/biopsy will be done at Screening (within 21 days prior to study drug administration) unless a bone marrow aspirate and biopsy was obtained within 12 weeks of starting study drug without intervening treatment and is representative of the subject's existing disease.
 - p. Serious adverse event assessment will be performed at Screening after informed consent has been obtained.
 - q. Adverse events will be followed until satisfactory clinical resolution of the adverse event is achieved.
 - r. Survival assessments will be collected every 3 months for 2 years following discontinuation from the study (including the extension portion of the study). In Protocol Amendment #12 this information will no longer be collected.

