3. Absence of constitutional symptoms.
4. Normal CBC as exhibited by:
 - Polymorphonuclear leukocytes $\geq 1,500/\mu\text{L}$.
 - Platelets $> 100,000/\mu\text{L}$.
 - Hemoglobin $> 11.0 \text{ g/dL}$ (untransfused).
5. Bone marrow aspirate and biopsy should be performed 2 months after clinical and laboratory results demonstrate that all of the requirements above have been met to demonstrate that a CR has been achieved. The marrow sample must be at least normocellular for age, with less than 30% of nucleated cells being lymphocytes. Lymphoid nodules should be absent. If the bone marrow is hypocellular, a repeat determination should be made in 4 weeks. Samples should be re-reviewed in conjunction with the prior pathology.

Partial Remission (PR) requires all of the following for a period of at least 2 months:

1. $\geq 50\%$ decrease in peripheral blood lymphocyte count from the pretreatment baseline value.
2. $\geq 50\%$ reduction in lymphadenopathy.
3. $\geq 50\%$ reduction in the size of the liver and/or spleen (if abnormal prior to therapy).

In addition **one or more** of the following criteria must be met:

- Polymorphonuclear leukocytes $\geq 1,500/\mu\text{L}$ or 50% improvement over baseline.
- Platelets $> 100,000/\mu\text{L}$ or 50% improvement over baseline.
- Hemoglobin $> 11.0 \text{ g/dL}$ or 50% improvement over baseline without transfusions.

Progressive Disease (PD) requires at least one of the following:

1. $\geq 50\%$ increase in the sum of the products of at least two lymph nodes on two consecutive determinations 2 weeks apart (at least one node must be $\geq 2 \text{ cm}$); appearance of new palpable lymph nodes.
2. $\geq 50\%$ increase in the size of the liver and/or spleen as determined by measurement below the respective costal margin; appearance of palpable hepatomegaly or splenomegaly, which was not previously present.
3. $\geq 50\%$ increase in the absolute number of circulating lymphocytes with at least $5,000/\mu\text{L}$.
4. Transformation to a more aggressive histology (e.g., Richter's syndrome or PLL with $> 55\%$ prolymphocytes).

Subjects who have not achieved a CR or a PR, or who have not exhibited PD will be considered to have Stable Disease (SD).

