5.3.3.1.2 IWCLL Updated NCI-WG Criteria – 2008

Methods of Measurement

Disease response and progression will be assessed by analysis of peripheral blood, clinical examination, radiographic techniques to assess splenomegaly, lymphadenopathy and/or bone marrow aspirate and biopsy to confirm active disease at baseline and if needed to confirm a CR.

All measurements should be taken and recorded in metric notation using a ruler or calipers. All baseline evaluations should be performed as closely as possible to the beginning of treatment and never more than 4 weeks before the beginning of the treatment.

The same method of assessment and the same technique should be used to characterize each identified and reported lesion at baseline and during follow-up.

Clinical lesions will only be considered measurable when they are superficial (e.g., skin nodules and palpable lymph nodes). For the case of skin lesions, documentation by color photography including a ruler to estimate the size of the lesion is required.

The diameter, in two planes, of the largest palpable nodes in each of the following sites should be measured: cervical, axillary, supraclavicular, inguinal, and femoral.

CT is the preferred method to measure lesions selected for response assessment. MRI may be used if medically indicated (e.g., severe contrast allergy). Conventional CT and MRI should be performed with cuts of 7 mm or less in slice thickness contiguously.

For accurate objective response evaluation, ultrasound (US) should not be used to measure tumor lesions. However, US is a possible alternative to clinical measurements of superficial palpable lymph nodes, subcutaneous lesions and thyroid nodules. US might also be useful to confirm the complete disappearance of superficial lesions usually assessed by clinical examination.

Assessment of response will be performed by the investigator and documented on the appropriate CRF.

Complete Remission (CR) requires all of the following for a period of at least 2 months:

1. Absence of clonal lymphocytes in the peripheral blood.
2. Absence of significant lymphadenopathy by physical examination and appropriate radiographic techniques. A CT scan of the abdomen, pelvis and thorax should be performed if previously abnormal. Lymph nodes should not be larger than 1.5 cm in diameter.

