3. No hepatomegaly or splenomegaly by physical examination. A CT scan of the abdomen should be performed at response assessment if found to be abnormal prior to the start of study drug or if physical exam is inconclusive at the time of evaluation.
4. Absence of constitutional symptoms.
5. Normal CBC as exhibited by:
 - Polymorphonuclear leukocytes $\geq 1,500/\mu\text{L}$ without G-CSF support.
 - Platelets $> 100,000/\mu\text{L}$.
 - Hemoglobin $> 11.0 \text{ g/dL}$ (untransfused or without erythropoietin support).

Bone marrow aspirate and biopsy should be performed at least 2 months after clinical and laboratory results demonstrate that all of the requirements above have been met to demonstrate that a CR has been achieved. The marrow should be analyzed by flow cytometry and/or immunochemistry to demonstrate that the marrow is free of clonal B-CLL cells. Note: cases with residual CLL cells by conventional flow cytometry or immunohistochemistry are defined as a PR.

Subjects who fulfill all the criteria for a CR, but who have persistent anemia, thrombocytopenia or neutropenia apparently unrelated to CLL, but related to drug toxicity should be considered as a different category of remission, CR with incomplete bone

marrow recovery (CRi). The marrow evaluation should be performed with scrutiny and not show any clonal infiltrate. Subjects should be monitored prospectively to determine whether or not their outcome differs from that of patients with detectable residual disease or with non-cytopenic PR.

Partial Remission (PR) requires at least two of the following for a period of at least 2 months:

1. $\geq 50\%$ decrease in peripheral blood lymphocyte count from the pretreatment baseline value.
2. $\geq 50\%$ reduction in lymphadenopathy (assessed by CT scan):
 - In the sum of products of up to 6 lymph nodes, or
 - In one lymph node diameter if only a single lymph node was present at baseline.
3. No increase in any lymph node, and no new enlarged lymph node. In small lymph nodes (< 2 cm), an increase of $< 25\%$ is not considered to be significant.
4. $\geq 50\%$ reduction in the size of the liver and/or spleen (if abnormal prior to therapy) as defined by CT scan.

In addition **one or more** of the following criteria must be met:

- Polymorphonuclear leukocytes $\geq 1,500/\mu\text{L}$ or 50% improvement over baseline without G-CSF support.
- Platelets $> 100,000/\mu\text{L}$ or 50% improvement over baseline.

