- Hemoglobin > 11.0 g/dL or 50% improvement over baseline without transfusions or erythropoietin support.

Progressive Disease (PD) requires at least one of the following:

1. Appearance of any new lesions such as enlarged lymph nodes (> 1.5 cm), splenomegaly, hepatomegaly or other organ infiltrates.

2. $\geq 50\%$ increase in the sum of the products of diameters of multiple nodes
3. $\geq 50\%$ in the greatest determined diameter of any previous site. A lymph node of 1-1.5 cm must increase by $\geq 50\%$ to a size greater than 1.5 cm in the longest axis. A lymph node of more than 1.5 cm must increase to more than 2.0 cm in the longest axis.
4. $\geq 50\%$ increase in the size of the liver and/or spleen or the de novo appearance of hepatomegaly or splenomegaly.
5. $\geq 50\%$ increase in the absolute number of blood lymphocytes with at least 5,000 B-lymphocytes per μL .
6. Transformation to a more aggressive histology (e.g., Richter's syndrome or PLL with $> 55\%$ prolymphocytes).
7. Occurrence of cytopenia (neutropenia, anemia or thrombocytopenia) attributable to CLL.
 - The progression of any cytopenia (unrelated to autoimmune cytopenia), as documented by a decrease of Hb levels by more than 2 g/dL or to less than 10 g/dL, or by a decrease of platelet counts by more than 50% or to less than 100,000/ μL , defines disease progression, if the marrow biopsy demonstrates an infiltrate of clonal CLL cells.

Subjects who have not achieved a CR or a PR, or who have not exhibited PD will be considered to have Stable Disease (SD).

A summary of the criteria described above is included in [Table 11](#).

Table 11. IWCLL Updated NCI-WG Criteria for Tumor Response (2008)

Criteria	Complete Remission (CR)	Partial Remission (PR)	Progressive Disease (PD)	Stable Disease (SD)
Lymphadenopathy	None above 1.5 cm	≥ 50% reduction	≥ 50% increase	Change of -49% to +49%
Hepatomegaly and/or Splenomegaly	Absent	≥ 50% reduction	≥ 50% increase or new hepatomegaly and/or splenomegaly	Change of -49% to +49%
Constitutional Symptoms	Absent	Present	Present	Present
Polymorphonuclear Leukocytes	≥ 1500/μL	≥ 1500/μL or > 50% improvement over baseline without G-CSF support	Not specified	Not specified
Circulating clonal B-lymphocytes	None	≥ 50% reduction from baseline	≥ 50% increase over baseline	Change of -49% to +49%
Platelets	> 100,000/μL	> 100,000/μL or ≥ 50% improvement from baseline	Decrease of ≥ 50% from baseline secondary to CLL	Change of -49% to +49%

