8.1.3.7 Reporting of Results

All subjects enrolled will be assessed for response to treatment based on the NCI-WG criteria in Section 5.3.3.1. Each subject will be assigned to one of the following categories: 1) complete remission, 2) complete remission with incomplete bone marrow recovery, 3) partial remission, 4) stable disease, 5) progressive disease, 6) early death from malignant disease, 7) early death from toxicity, 8) early death because of other cause, or 9) unknown (not assessable, insufficient data).

Subjects in response categories 5-8 will be considered as failing to respond to treatment (disease progression). Thus, an incorrect treatment schedule or drug administration will not result in exclusion from the analysis of a response.

Sub-analyses may be performed on the subset of subjects for whom major protocol deviations have not been reported (e.g., early discontinuation of treatment, major protocol violations, etc.). The reasons for excluding subjects from the analysis will be clearly reported.

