For a given subject, PFS was defined as the number of days from the date the subject started study drug to the date the subject experiences an event of disease progression, or to the date of death if disease progression was not reached. All events of disease progression were included, regardless of whether the event occurred while the subject was still taking study drug or had previously discontinued study drug. Events of death were included for subjects who had not experienced disease progression provided the death occurred within 2 cycles (42 days) of the date of the last available tumor evaluation. If a subject had not experienced an event of disease progression or death as defined above, then the subject's data was censored at the date of the last available evaluation for disease progression. The date of the last available evaluation was the date of the last study visit at which a tumor assessment was performed.

Response Rate

- Objective Response Rate (ORR)
 - Phase 1: $ORR = CR + PR$.
 - Phase 2: $ORR = CR + CR_i + PR$.

- Best Response Rate
 - Phase 1: Complete Response (CR), Partial Response (PR), Stable Disease (SD), Disease Progression (PD), and Incomplete Data (ID) were reported.
 - Phase 2: Complete Response (CR), Complete Response - incomplete bone marrow (CRi), Partial Response (PR), Stable Disease (SD), Disease Progression (PD), and Incomplete Data (ID) were reported.
- Disease Control Rate (DCR)
 - Phase 1: $DCR = CR + PR + SD$.
 - Phase 2: $DCR = CR + CRi + PR + SD$.

The exact binomial distribution was used to construct this confidence interval for the response rates, and the corresponding 95% confidence interval was constructed.

Time to Tumor Progression

Time to tumor progression for a given subject was defined as the number of days from the date the subject started study drug to the date of the subject's tumor progression. Time to tumor progression was collected up to 2 cycles (42 days) following the date of the last available tumor evaluation. All events of tumor progression were included, regardless of whether the event occurred while the subject was still taking study drug, or after the subject discontinued study drug. If a subject had not progressed, then the data was censored at the date of the last study visit at which a tumor assessment was performed.

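### The SAP's disease control rate accepts stable disease at any time, so an unchanged tumor assessment before the end of Cycle 2 can count as disease control

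*SAP*

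**What the plan says.** **The measure.** The SAP (Response Rate) gives DCR for Phase 2 as "DCR = CR + CRi + PR + SD", and for Phase 1 as CR, PR and SD. It attaches an exact binomial 95% interval. Under Exploratory Efficacy, analyses are shown by dose level and overall. Under Data Sets Analyzed, anyone who took one dose is in the efficacy summaries: 29 subjects in Phase 1 and 31 in Phase 2. DCR is not among the endpoints in protocol Sections 5.3.3 or 8.1.3.

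**Stable disease.** Protocol Section 5.3.3.1.2 (2008 criteria) says "Subjects who have not achieved a CR or a PR, or who have not exhibited PD will be considered to have Stable Disease", and Section 5.3.3.1.1 (1996 criteria) has the same rule. Table 11 adds an SD column with bands such as "Change of -49% to +49" percent. None of these has a time element.

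**CR and PR, for contrast.** Section 5.3.3.1.2 says "Complete Remission (CR) requires all of the following for a period of at least 2 months" and "Partial Remission (PR) requires at least two of the following for a period of at least 2 months". The 1996 criteria also set 2 months for both.

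**Timing.** Footnote k of Tables 1 to 3 says "Assessment for tumor response will be performed at the end of Cycle 2, end of Cycle 4", then lists later cycles and the Final Visit. Section 5.4.1 asks for discontinuation procedures promptly after stopping, with a tumor assessment only if needed.

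**Response classes.** The SAP's best-response list is CR, CRi (Phase 2 only), PR, SD, PD and Incomplete Data, the last without a definition. Protocol Section 8.1.3.7 has nine categories. Three are early deaths (6 malignant disease, 7 toxicity, 8 other cause), and it adds: "Subjects in response categories 5-8 will be considered as failing to respond to treatment (disease progression").

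**The concern.** DCR is meant to show how many subjects had their disease held in check for a meaningful time. If SD can be scored at any moment after the first dose, a subject who leaves in the first weeks and has not yet changed from baseline is credited with control that nobody had time to observe. CR and PR are protected against this by their 2-month requirement; SD is not.

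The rate is reported with an exact interval and by dose level, so it invites comparison between doses. In cohorts of about three, one early leaver moves the rate a long way, always upward. The missing early-death categories add a related problem: some subjects whom the protocol calls failures have no failure class in the SAP's table.

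**Working it through.** The documents state no DCR value, target or sample size based on it, so there is no figure to reproduce. The check covers the definition and the weight of one subject.

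**1. Does an unchanged early assessment meet SD?** Take a subject who stops before the end of Cycle 2, has a Final Visit tumor assessment under footnote k, and shows no qualifying response or progression.
- Residual rule (1996 and 2008): not CR, not PR, not PD, hence SD.
- Table 11 bands: an unchanged value lies inside them, and no duration is asked.
- Efficacy set: one dose is enough, so the subject is in the denominator.
- DCR: SD is in the numerator, so the subject counts as controlled.

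The SAP applies the 1996 criteria to Phase 1, while protocol Section 5.3.1.1 (Tumor Assessments) uses the 2008 criteria there. SD is residual under both, so the result is the same.

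**2. When is the first routine assessment?** Cycle length is 21 days and the planned lead-in on the 21/21 schedule is 7 days (Section 5.1).
- 14/21 schedule: 2 × 21 = day 42.
- 21/21 schedule: 7 + 42 = day 49. If the lead-in runs to 14 days: 14 + 42 = day 56.

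**3. Weight of one such subject.**
- Phase 2: 1/31 = 3.2 points.
- Phase 1 overall: 1/29 = 3.4 points.
- A Phase 1 cohort at the stated minimum of three: 1/3 = about 33 points.

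**4. Illustration.** The number of such subjects, k, is not in the documents. Assume 16 subjects count as controlled without them (also an assumption) and let k vary. Intervals are exact (Clopper-Pearson) 95%.

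| k | Phase 2, (16 + k)/31 | Phase 1, (16 + k)/29 |
|---|---|---|
| 0 | 51.6% (33.1 to 69.8) | 55.2% (35.7 to 73.6) |
| 1 | 54.8% (36.0 to 72.7) | 58.6% (38.9 to 76.5) |
| 3 | 61.3% (42.2 to 78.2) | 65.5% (45.7 to 82.1) |
| 5 | 67.7% (48.6 to 83.3) | 72.4% (52.8 to 87.3) |

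With k = 3 the shift is 3/31 = 9.7 points in Phase 2 and 3/29 = 10.3 in Phase 1.

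**5. Early deaths, side by side.** Section 8.1.3.7 counts categories 5 to 8 as failures; the SAP list keeps only PD from that group.
- Death from disease progression in Phase 2a: Section 5.3.3.1.3 names it as clinical disease progression, so it can reach PD.
- Early death from toxicity or another cause: no failure class in the SAP. It would fall in Incomplete Data, or in SD (and so in DCR) if an unchanged assessment came first.

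**The case against.** The best counter-argument is that the documents do not show these subjects being scored as SD in practice.

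- Section 5.4.1 makes the discontinuation tumor assessment conditional.
- Section 5.3.3.1 says response is judged while treatment continues.
- Footnote k takes the blood for response on Day 1 of the next cycle, a visit an early leaver may not have.
- Table 11's SD column includes an unchanged marrow, and marrow is not routinely repeated that early.

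An early leaver could therefore be classed as Incomplete Data. This stands in part: a subject with no assessment could well go there. But footnote k does schedule a Final Visit assessment, and since Incomplete Data has no definition, nothing directs an assessed, unchanged subject away from SD.

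Three stronger readings are tempting and are not supported:

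- **That Incomplete Data cannot catch these subjects.** It is undefined, so the documents do not settle this either way.
- **That an early stop for thrombocytopenia is the typical case.** Entry requires platelets of at least 75,000/mm³ and dosing is interrupted or stopped below 25,000/mm³. From 75,000 that is a fall of more than 1 − 25/75 = 66.7%, outside Table 11's platelet band for SD unless counts recover by the Final Visit. Only the residual sentence would then make the subject SD. Sections 6.7.1 and 6.7.2 also allow interruption and restart, so a permanent stop is not the only path.
- **That early intolerance has been shown to inflate DCR.** The 3.2 and 3.4 points are differences between two definitions. Someone who would have been stable at Cycle 2 anyway is not a false success.

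It is also fair that DCR is exploratory, that no hypothesis or sample size rests on it, and that the SAP's exposure table by number of cycles gives readers some view of early stops.

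**Conclusion.** The point holds as a gap in definition. As written, SD counts toward DCR however early it is seen, and an assessed, unchanged subject who stops before the end of Cycle 2 qualifies. The effect on the reported rate can only be upward: each such subject carries the weight in step 3, against a count the documents do not give. This assumes that the Final Visit assessment was done and that the subject was not placed in the undefined Incomplete Data class.

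The early-death omission is a separate departure from Section 8.1.3.7. A reader might infer that every early death loses its failure status and that the PD count is too low throughout. That goes too far: Phase 2a deaths from disease progression have a route to PD. The gap is clear for toxic and other-cause early deaths. Those that land in Incomplete Data stay in the denominator and do not raise DCR.

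The consequence is limited to an exploratory descriptive rate in an uncontrolled study. ORR and PFS do not treat SD as success, and Section 6.7.5 bases the recommended Phase 2 dose on DLTs and the MTD.

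**What to change.** In the SAP:

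1. Count SD as best response, and toward DCR, only if it is documented at or after the scheduled end-of-Cycle-2 assessment. State the visit window, since footnote k gives none.
2. Define Incomplete Data (or not evaluable) to include subjects whose only assessments came earlier and showed no PD, and subjects with no post-baseline assessment. Keep them in the denominator and do not count them as controlled.
3. Show early-death categories 6 to 8 in the best-response table as failures, as Section 8.1.3.7 requires.

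The SAP is written in the past tense with final subject numbers. If results are already final, report this as a sensitivity analysis beside the existing DCR, together with the number of SD subjects assessed only before the end of Cycle 2.

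The cost is a few sentences and a rerun of one table. The assessment and death dates are already needed for PFS and OS. The reported DCR may be a few points lower.
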